10.4.7 PLANNED INTERIM ANALYSES

There is no planned formal interim analysis

10.5 SAMPLE SIZE OVERALL

This pilot study is powered to show a difference of at least 7 B-lines between treatment arms. With a total of 70 subjects (i.e. 35 in each arm), we will have 82% power to detect an effect size of 0.7 on the number of B-lines, where the type I error rate is controlled at 0.05 (two sided)..

Local Sample Size: As a multicenter study, the expected enrollment at IU is half the patients or 35. However, up to 50 patients may be enrolled depending on accrual rates at the other site.

10.6 MEASURES TO MINIMIZE BIAS

10.6.1 ENROLLMENT/ RANDOMIZATION/ MASKING PROCEDURES

Each site will be provided a block randomization table with variable block sizes of 2, 4, and 6. The data coordinating center will continuously monitor the recruitment until the targeted sample size is reached. We will utilize the REDCap Randomization module for web-based randomization.

Due the nature of the intervention and the clinical setting, this is an unblinded trial.

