- That I will be responsible for maintaining each patient's consent form in the study file and provide each patient with a signed copy of the consent form.

Investigator Name and Title:

Institution Address:

Signature: _____

Date: _____

PROTOCOL SUMMARY

Title: *"Nitroglycerin vs. Furosemide using Lung Ultrasound Pilot Trial" (N-FURIOUS)*

[figure not shown]
Précis: Of the one million admissions for AHF in the US, approximately 80% are initially managed in the ED. Outcomes from AHF are poor: nearly 25% are dead or re-hospitalized within 30 days of discharge. The evidence base to treat AHF is limited. In fact, there are no pharmacologic therapies with Class I, Level A guideline recommendations. The acute

treatment of patients today is largely the same as 40 years ago. This proposal aims to build the evidence base for ED AHF care.

Using a two-site, randomized controlled design, this pilot study will test whether a nitrate intense strategy more effectively reduces congestion, defined by LUS B-lines, better than a diuretic intense strategy.

Objectives:	1: To determine whether a nitrate intense strategy safely reduces congestion, defined by LUS B-lines, better than a diuretic intense strategy. 2: To demonstrate feasibility of recruitment and compliance with study protocol to inform future study design and enrollment projections, an external site will also test our study protocol.
Endpoint	A comparison of total B-lines at the conclusion of ED AHF management or maximum of 6 hours after enrollment, whichever comes first.
Population:	Emergency department (ED) AHF patients. All patients who meet inclusion and no exclusion criteria will be enrolled during their ED visit within 3 hours of presentation.
Phase:	2
Number of Sites enrolling participants:	Two sites (3 total hospitals). Projected sample size, n=70.
Description of Study Agent:	Nitrate intense vs. Diuretic intense AHF treatment strategy
Study Duration:	2 years. There will be three months of start up, and one month of study conclusion work. Enrollment will occur over 20 months, which equals 3.5 patients month. As there will be staggered start up to determine replication, approximately 1-2 patients/month.
Participant Duration:	30 days post discharge

SCHEMATIC OF STUDY DESIGN

*whichever comes first

**Presentation is defined as first time recorded when placed in a room to be treated. This allows patients to still be enrolled despite a long waiting room time

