4 STUDY DESIGN AND ENDPOINTS

4.1 DESCRIPTION OF THE STUDY DESIGN

A two-site, prospective, randomized, pilot trial comparing a nitrate intense vs. diuretic intense strategy. All potential ED patients will receive an initial LUS scan. Performing LUS is within the standard of care and will be done at no cost to patients. It is not frequently used however, either for diagnosis, prognosis, or to guide clinical therapy. However, treating clinicians will be blinded to these results. If clinicians choose to perform their own LUS, those patients will not be excluded. Patients who provide written informed consent and meet all inclusion and no exclusion criteria will be randomized 1:1 to either study arm. For randomized patients, study protocol will continue until there is a decrease in B-

lines to ≤ 15 or 6 hours of care has been delivered. Subjects who are hospitalized prior to the completion of the 6 hour protocol may continue on the protocol until the six hour treatment window is concluded. All images will be stored and overread by an independent, expert ultrasonographer blinded to treatment arm.

Safety of patients are paramount. If a potential life threatening etiology is identified, the clinical team will be made aware immediately, irrespective of randomization arm. These occurrences will be recorded in the eCRF. While this will be a rare event, we will a priori establish that an additional patient will be accrued into the study and an additional modified intent to treat population for analysis will be performed, excluding these patients where a life-threatening etiology was identified (i.e. pericardial tamponade).

For patients who do NOT meet eligibility criteria, the results of their LUS will be provided to the clinical team as requested.

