10.2 STATISTICAL HYPOTHESES

- *Hypothesis 1a: Nitrate intense treated patients will have less congestion, defined by LUS B-lines, than diuretic intense patients at 6 hours after start of treatment.*
- *Hypothesis 1b: Nitrate intense treated patients will have greater dyspnea relief than diuretic intense patients at 6 hours after start of treatment.*
- *Hypothesis 2: Each site (n=3) will enroll ~2 patient per month for 12 months.*

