10.4.3 ANALYSIS OF THE PRIMARY EFFICACY ENDPOINT(S)

The total number of B-lines at the conclusion of ED AHF management

We will examine the distribution of B-lines measurements for the groups with and without events separately. Both absolute number and relative change will be evaluated. Receiver Operating Characteristic (ROC) curves will be plotted together with area under the curve (AUC) calculated to understand the prediction performance of the B-line measurements. Sensitivity, specificity, positive and negative predictive values will be computed at a number of thresholds of B-line measurements to understand the trade-off between false positive and false negative. Confidence intervals of statistical measures will be constructed using the bootstrap method.⁹¹ Although 15 B-lines have been previously identified as a valid threshold, an alternative number may be more useful in the ED setting.

Potential covariates will also be considered in a logistic regression setting to improve precision, which includes baseline co-morbidities, baseline medications (in particular guideline recommended therapies) in-hospital medications, baseline renal function, serum sodium, natriuretic peptide levels, troponin levels, renal function, baseline blood pressure, and discharge medications. Variables such as physical exam, other vital signs, and hemoconcentration may also be included. These covariates are known markers of risk and are standard of care assessments for the vast majority of AHF admissions. Covariates with univariately significant association with the outcome will be included together with the treatment indicator in a logistic regression model. Due to limited sample size, we will limit the number of covariates (including treatment indicator) such that there is 10 events per covariate.

ANALYSIS OF THE SECONDARY ENDPOINTS

1. Dyspnea will also be assessed using a 5-point and 7-point Likert scale.

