Dyspnea will be assessed at the baseline and 6 hours later (or closest time point prior to ER discharge using two instruments. Dyspnea will also be assessed at any time between D2 and D/C. A 7-point Likert scale to determine change from baseline: 1) markedly worse, 2) moderately worse, 3) minimally worse, 4) no change, 5) minimally improved, 6) moderately improved, 7) markedly improved. However, patients may not recall accurately how they felt at baseline or be uncertain about when baseline was supposed to be. Also, patients with severe symptoms who don't respond and patients whose symptoms were initially mild and have little room to improve may end up with similar change scores. Accordingly, symptoms were also assessed using an absolute scale. Change in dyspnoea can be calculated by subtracting scores. A 5-point Likert scale was used to document patients' current status: 1) not short of breath at all, 2) mildly short of breath, 3) moderately short of breath, 4) severely short of breath, 5) very severely short of breath.

Patients were placed at 45 degrees for all questioning. If patients were recently up and walking, at least 2 minutes of equilibration is required.

Change scores between responses at baseline and 6 hours on the 5-point Likert scale items and the VAS were calculated by subtracting the baseline value from the 6-hour value. These change scores were categorized as improvement, worsening and no change. Fisher's exact tests were used to compare the 3 groups by either definition on changes in the 5-point Likert scale

2. The comparison of binary endpoints (B-lines ≤ 15) will be performed using Chi-square or Fishers exact test, as appropriate.

As 15 B-lines have been previously shown to be associated with worse outcomes, a difference of 15 B lines will be considered significant for this study.

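### Randomisation is blocked separately by site, but no planned treatment comparison includes site; the effect is conservative and probably small, and the remedy is nearly free.

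*Combined protocol and SAP*

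**What the plan says.** **Allocation.** Section 4.1 says that consenting, eligible patients "will be randomized 1:1 to either study arm". Section 10.6.1 adds: "Each site will be provided a block randomization table", with block sizes varying among 2, 4 and 6. Site is therefore a stratification factor by design.

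**Primary endpoint (10.4.3).** The section describes distributions, ROC curves, classification measures, bootstrap intervals and a logistic model. It names no between-arm test or model for the final B-line count. Site and hospital are absent from the candidate covariates, and entry is data-driven: "Covariates with univariately significant association with the outcome will be included together with the treatment indicator in a logistic regression model". The number of covariates is also capped by an events-per-covariate rule.

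**Secondary endpoints (under 10.4.3).** "The comparison of binary endpoints (B-lines ≤ 15) will be performed using Chi-square or Fishers exact test, as appropriate". Dyspnoea change categories are compared by Fisher's exact test. Neither test is stratified.

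**Exploratory and safety analyses (10.4.4, 10.4.5).** These use unstratified t, Wilcoxon, chi-square or Fisher tests. The proportional odds model for days alive and out of hospital permits baseline covariates but names none. The one mixed model has patient and observer random effects and serves reproducibility only.

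**Sample size (10.5).** This is a plain two-group calculation: "With a total of 70 subjects (i.e. 35 in each arm"), with 82% power for an effect size of 0.7.

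**What a site is.** The Protocol Summary has "Two sites (3 total hospitals). Projected sample size, n=70". Section 10.2 has "Each site (n=3) will enroll ~2 patient per month for 12 months". Section 10.5 speaks of the coordinating institution and one other site.

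**The concern.** Blocking within site keeps the arms balanced within each site, so between-site differences in B-lines largely cancel from the treatment difference. An analysis that ignores site still counts those differences in the residual variance. Its standard error then describes a less precise experiment than the one run.

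The outcome is a count read from images that depend on operator and machine. Section 17.3 prefers common equipment but allows sites to use different machines, with gain then standardised within each site. Training is led by each site's own ultrasound lead. Case mix may also differ. Site could therefore carry some of the outcome variance, and a 70-patient trial has little precision to spare. At stake is a modest loss of power and an interval somewhat wider than necessary in a pilot meant to inform a definitive trial.

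**Working it through.** **Inputs from section 10.5.** 35 per arm; difference 7 B-lines; effect size 0.7, so the implied SD is 7/0.7 = 10 (the SD itself is not stated); two-sided alpha 0.05; stated power 82%. No dropout allowance is given and none is used.

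**Assumed.** ρ, the share of total outcome variance between sites, is not in the documents and is varied from 0 to 0.20. The SD of 10 is taken to include between-site variance.

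**Step 1: reproduce the plan's figure.** For a two-sample t test, the noncentrality is d√(n/2) = 0.7 × √17.5 = 2.928 on 68 df. Power is 82.3%, which agrees with the stated 82%. So the plan's figure contains no site term.

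**Step 2: add a fixed site effect.** The residual SD becomes 10√(1−ρ), so d becomes 0.7/√(1−ρ), on 70−1−k df for k units. With k = 2 (k = 3 is within 0.1 point):

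| ρ (assumed) | d | Power with site | 95% half-width, B-lines |
|---|---|---|---|
| 0 | 0.700 | 82.3% | 4.77 |
| 0.01 | 0.704 | 82.7% | 4.75 |
| 0.02 | 0.707 | 83.0% | 4.72 |
| 0.05 | 0.718 | 84.2% | 4.65 |
| 0.10 | 0.738 | 86.0% | 4.53 |
| 0.20 | 0.783 | 89.7% | 4.27 |

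Without site, the half-width is t × 10 × √(2/35) = 4.77 throughout. It is therefore too wide by 4.77/4.65 − 1 ≈ 2.6%, 4.77/4.53 − 1 ≈ 5.3% and 4.77/4.27 − 1 ≈ 11.7% at ρ = 0.05, 0.10 and 0.20. At ρ = 0 the exact powers are 82.30% without the term, 82.28% with two units and 82.26% with three, so the cost is under 0.1 point.

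**Step 3: check by simulation.** Blocks of 2, 4 and 6 were generated within site, with 4,000 runs per setting. The splits were 35/35 and 50/20 (both from 10.5) and 35/18/17 (assumed, for three units).

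| ρ | Analysis | Type I error | Coverage |
|---|---|---|---|
| 0.10 | no site term | 3.9–4.2% | 95.8–96.4% |
| 0.20 | no site term | 2.7–3.1% | 96.6–97.4% |
| 0.10 and 0.20 | site term | 4.5–5.2% | 94.4–95.5% |

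The Monte Carlo standard error of a 5% rate is √(0.05 × 0.95/4000) ≈ 0.34 point. At ρ = 0.05 the departures from nominal are not clearly distinguishable from that noise.

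**Step 4: the gain over the analysis actually run.** Under site blocking, the unadjusted test already benefits a little from the balance. Its simulated power for a 7-line difference is 82.4–84.3% at ρ = 0.10 and 84.3–85.1% at ρ = 0.20. Within each split, the site term adds 0.9–1.5 points at ρ = 0.05, 2.4–3.1 at 0.10 and 4.9–5.0 at 0.20. The change from 82.3% in Step 2 therefore somewhat overstates the practical gain.

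**The case against.** **Sites may hardly differ.** Sections 17.1 to 17.3 work against site differences: a common training format, fixed depth, a low-frequency curvilinear probe, a preference for the same machine, regular feedback, and blinded central reading of images stripped of site identity and mixed across sites. A reader might infer from 17.3 that machines and settings do differ, so that counts are likely to. The text supports only that they may differ. Central reading cannot remove differences in acquisition or case mix, so the possibility stands, but its size is unknown and may be negligible.

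**Baseline adjustment may absorb much of it.** Section 17.3 keeps the same machine and settings for serial scans, so a machine offset would appear in the baseline count too. The powers above credit site alone, without baseline. Once baseline B-lines are in the model, site may add less. This stands.

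**No primary test or interval is named.** A reader might infer that the planned confidence intervals contradict the design. Section 10.4.3 specifies no interval for the treatment difference; its bootstrap sentence follows the ROC and classification measures. The error term used here is the one implied by 10.5. The missing primary model is the larger gap, and site belongs in its repair.

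**The covariate wording is open.** Section 10.4.3 says that further variables may be added, and the proportional odds model allows covariates. Neither commits to site, and a significance screen is the wrong test for a design factor. This objection fails.

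**Conclusion.** The mismatch is real: allocation is stratified by site and no planned treatment comparison is. Its consequence is limited to lost precision, and only if sites differ. A reader might infer bias or too many false positives; the simulation shows neither, since the unadjusted test is conservative (type I error 2.7–4.2% at ρ of 0.10 to 0.20).

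The size rests on an assumed ρ, on the t test implied by 10.5, on an SD of 10 that includes site variance, and on no baseline adjustment. Under those assumptions the effect is negligible at ρ of 0.02 or less and modest from 0.05 to 0.20.

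A reader might also conclude that hospital, with three levels, is the factor to fit. The documents do not settle that, because they count two sites, three hospitals and three sites in different places. Severity is minor to moderate for a 70-patient pilot.

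**What to change.** 1. State in 10.6.1 whether each block table belongs to a site or to a hospital, and reconcile the Protocol Summary, 10.2 and 10.5 with it.
2. In 10.4.3, prespecify a linear model for the between-arm difference in final B-line count, with treatment, the randomisation unit as a fixed factor, and baseline B-lines. The unit should enter regardless of any significance screen.
3. For B-lines of 15 or fewer, use a Cochran-Mantel-Haenszel or stratified exact test by the same unit.
4. If a bootstrap interval is reported for the treatment difference, resample within that unit.

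The cost is SAP wording and one degree of freedom for two units, or two for three, beyond the baseline term. No new data are needed, and the sample size is unchanged.

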7.3 STUDY SCHEDULE

7.3.1 SCREENING

A signed and dated informed consent form will be obtained before any study-specific screening procedures are performed. Results of evaluations obtained as part of routine medical care, which are performed prior to obtaining informed consent, may be used in place of the protocol-specified evaluations. Patients will acknowledge and agree to the use of this information for the study by giving informed consent.

At the Baseline Visit, patients will be assigned by the Internet Web-based Randomization System (IWRS) a unique permanent identification number (referred to as the patient identification number) such that all randomized patients from each center are given consecutive identification numbers by the IWRS in successive order of inclusion. We will utilize the REDCap randomization module.

Prospective study patients will have presented to the hospital for urgent therapy for AHF. Potential patients will be identified either en route to or upon arriving at the ED/hospital. Routine assessments associated with usual patient care may be used for the purposes of screening and may be completed in any order. Study specific procedures must be completed only after Informed Consent is obtained.

Patients may be enrolled at anytime during their ED stay, but preferably within 3 hours of first placement in a room in the emergency department. Time spent in the waiting room will not count towards these 3 hours.

The following procedures will be performed prior to or during Screening:

- Obtain written informed consent (must be performed as the first study-specific procedure)
- Review of prior medical history
- Review of prior and concomitant medications
- Physical examination (including height and weight when reasonably possible)
- Vital signs measurements (includes systolic and diastolic blood pressures, heart rate, body temperature, oxygen saturation reading and respiratory rate)
- 12-Lead Electrocardiogram
- Chest X-Ray (this is not a requirement however, for inclusion)
- Blood collection for local laboratory tests, including BNP or NT-proBNP, and pregnancy test if applicable.
- Inquiry about Adverse events

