7.3.2 ENROLLMENT/BASELINE

Patients who continue to fulfill all of the eligibility criteria will be randomized. In regards to the SBP; a single recording below 120mmHg does NOT disqualify the patient as long as the SBP returns > 120mmHg. Randomization will occur via central IWRS system.

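### Section 10.6.1 gives each site a block table and prints the block sizes of an unblinded trial, without reconciling this with central web randomisation or saying that list and sizes are hidden from recruiters

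*Combined protocol and SAP*

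**What the plan says.** Section 10.6.1 is the plan's section on enrolment, randomisation and masking. Its first sentence says "Each site will be provided a block randomization table" with "variable block sizes of 2, 4, and 6". It then gives the delivery method, "We will utilize the REDCap Randomization module for web-based randomization", and closes with "Due the nature of the intervention and the clinical setting, this is an unblinded trial".

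Two other places describe delivery. Section 7.3.1 says "We will utilize the REDCap randomization module" and has the IWRS number randomised patients consecutively within each center. Section 7.3.2 says "Randomization will occur via central IWRS system".

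Section 12 makes the PI responsible for explaining the protocol to all study staff, so block sizes printed in it reach the people who recruit. No section says who generates or keeps the list, that recruiters cannot see future assignments, or that block sizes are withheld.

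**The concern.** Blocking protects balance, but it protects against selection only if the next assignment cannot be foreseen. Here treatment is open, so past assignments at a hospital are visible to its staff. The blocks are small and their sizes are printed. One sentence, read literally, sends the table itself to the site.

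Entry leaves some room for judgement. AHF is a clinical diagnosis (5.1, 5.2), and a single systolic reading below the cut-off does not disqualify a patient if the pressure recovers (7.3.2). The T00 scan is used for eligibility and its B-lines are counted by trained research personnel (7.3.4, 17.3), so study staff can know the baseline value of the primary measure before randomisation. A recruiter who expects a given arm could choose not to enrol a particular patient.

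The blinded image overread (4.1, 17.3) protects how scans are read, not who enters which arm. Section 10.4.3 prespecifies no baseline-adjusted comparison of final B-line totals between arms that might absorb part of an imbalance.

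**Working it through.** **The plan's own figure.** The plan gives no figure for predictability. Its one design figure is 82% power with 35 per arm, effect size 0.7 and two-sided 0.05 (10.5). A two-sample t test with 68 degrees of freedom and noncentrality 0.7 × √(35/2) = 2.93 gives 82.3%, so that figure is reproduced. It is unaffected by this point.

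**Inputs.** 1:1 allocation (4.1); blocks of 2, 4 and 6 (10.6.1); 70 patients at two sites comprising three hospitals (Protocol Summary); 35 expected at the lead site, up to 50 (10.5). Section 10.2 counts three sites, so the number of lists is unclear. I take 70/3 ≈ 23, 35 and 50 patients per list. The plan gives no mix of block sizes; equal use is my assumption, and other mixes are shown.

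**Case 1, table readable at the site.** All upcoming assignments are known: 100%.

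**Case 2, table unseen, sizes known, treatment open.** One step can be done by hand. After the first patient on a list, the second is in the other arm with probability 1 for a block of 2, 2/3 for a block of 4 and 3/5 for a block of 6:

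(1 + 2/3 + 3/5)/3 = 75.6%.

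For whole lists I simulated permuted blocks. The guesser knows the sizes and past assignments but not the block boundaries, updates the probabilities after each patient and picks the likelier arm.

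| Blocks, patients per list | Correct | Certain | Called at ≥75% |
|---|---|---|---|
| 2/4/6, 23 | 69.2% | 3.7% | 57.1% |
| 2/4/6, 35 | 69.5% | 3.9% | 57.8% |
| 2/4/6, 50 | 70.1% | 4.0% | 59.3% |
| 2/4/6 mixed 0.5/0.3/0.2, 35 | 70.5% | 2.7% | 56.2% |
| 2/4/6 mixed 0.2/0.3/0.5, 35 | 68.9% | 5.3% | 50.3% |
| 4/6/8, 23 | 66.8% | 2.3% | 36.1% |
| 4/6/8, 35 | 67.4% | 2.4% | 35.7% |

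Simple randomisation would give 50% correct.

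**Case 3, boundaries also known.** Expected correct guesses per block are 1.5 of 2, 2.833 of 4 and 4.1 of 6, so (1.5 + 2.833 + 4.1)/12 = 70.3%. Certain assignments are (1 + 1.333 + 1.5)/12 = 31.9%.

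**What the block of 2 contributes.** At 35 per list, moving to 4/6/8 lowers correct guesses by 69.5 − 67.4 = 2.1 points and calls at 75% or better from about 58% to about 36%. That second fall depends on the cut-off. At a two-thirds cut-off the shares are 57.8% and 58.7%, because many calls under 2/4/6 sit near 75.6%, while the matching second-patient call under 4/6/8 is (2/3 + 3/5 + 4/7)/3 = 61.3%.

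**Scale in B-lines (illustration).** Suppose staff could shift the expected final count of every enrolled patient by δ in the direction of the guess. With guess accuracy p, the spurious difference between arms is 2δ(2p − 1). For p = 0.692, δ = 2.5 gives 5 × 0.384 = 1.9 B-lines and δ = 5 gives 3.8. With the table readable (p = 1), δ = 2.5 gives 5.0. The target difference is 7 (10.5). The values of δ are assumptions; the documents give none.

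**The case against.** The strongest objection is that allocation is central. Section 10.6.1 names the REDCap module two sentences after the table sentence, and 7.3.1 and 7.3.2 agree. The table sentence may only mean that each site has its own stratum in the system. That reading is reasonable, and it rules out presenting the 100% case as fact. It does not settle the matter, because no text says the list is hidden, and the guessing in case 2 remains under it.

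A second objection is that entry has measured limits: more than 15 B-lines in at least 4 zones, blood pressure and eGFR cut-offs, and no entry exceptions (5.1, 5.2, 12). Accrual is also slow, about 3.5 patients a month overall (Protocol Summary) and about 2 per site per month (10.2), and enrolment must fall within the ED stay. This largely stands. A reader might infer that staff could hold a patient until a preferred slot comes up, but another patient would have to take the unwanted slot meanwhile, which is implausible at this rate. The realistic route is not enrolling someone.

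Third, 69% is the accuracy of a diligent guesser, not a bias. That is correct. The B-line illustration rests on an assumed strength of steering applied to every patient.

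**Conclusion.** The point holds as an unreconciled and incomplete description of allocation concealment, with block sizes disclosed in an open trial. It should be corrected.

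If the table is kept from site staff, about 69 to 70% of assignments can be guessed correctly, about 4% are certain, and about 58% can be called with at least 75% confidence. This assumes equal use of the sizes, 23 to 35 patients per list, and a guesser who knows the sizes and every past assignment on the list. Over the other mixes and list lengths run, the ranges are 68.9 to 70.5%, 2.7 to 5.3% and 50 to 59%.

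A reader might infer three stronger things that the documents do not support:

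- That sites know upcoming assignments. This follows only if they can read the table.
- That the block of 2 is the main fault. Removing it alone lowers average correct guessing by about 2 points; most of the predictability comes from small blocks with known sizes under open treatment.
- That enrolment was steered. The documents show only that it could be.

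**What to change.** Replace the table sentence in 10.6.1 with wording such as: *The allocation list, stratified by site, is generated and held by the data coordinating center, loaded into REDCap and not released to any site; each assignment is revealed only after consent and confirmed eligibility.* Use the same description in 7.3.1 and 7.3.2, and say whether a stratum is one of the two sites or one of the three hospitals.

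Move the block sizes to a restricted document that recruiting staff do not receive. These two changes bring most of the gain, and their cost is wording.

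For any list not yet in use, also drop the block of 2, for example by using 4, 6 and 8. At 35 per list this takes average correct guesses to about 67% and calls at 75% or better to about 35 to 36%. The cost is regenerating the list and a slightly larger possible imbalance within a site at the end of the trial. The documents do not say whether lists are already in use. Replacing one mid-trial is more than a wording change, so this step should be limited to unused lists.
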